3. Subjects with Fitzpatrick Skin Type IV, V, or VI
4. Subjects with moderate to severe acne as defined by investigator-assessed Global Acne Assessment Score (GAAS) of 3 or 4 at screening
5. Facial acne vulgaris with 20 to 50 (inclusive) inflammatory lesions and 30 to 100 (inclusive) noninflammatory lesion
6. Stable non-progressive or regressive acne vulgaris in the investigator's opinion

7. Females of childbearing potential (FCBP) must have a negative pregnancy test at Screening and Baseline. A female is considered not to be of childbearing potential if she is post-menopausal with at least 12 consecutive months of amenorrhea or has undergone surgical sterilization. While on investigational product and for at least 28 days after taking the last dose of investigational product, FCBP who engage in activity in which conception is possible must use one of the approved contraceptive options described below:

Option 1: Any one of the following highly effective methods: hormonal contraception (oral, injection, implant, transdermal patch, vaginal ring); intrauterine device (IUD); tubal ligation; or partner's vasectomy;

OR

Option 2: Male or female condom (latex condom or nonlatex condom NOT made out of natural [animal] membrane [for example, polyurethane]); PLUS one additional barrier method: (a) diaphragm with spermicide; (b) cervical cap with spermicide; or (c) contraceptive sponge with spermicide.

8. Must be in general good as judged by the Investigator
9. Subject is willing to avoid excessive or prolonged exposure of the treated skin to ultraviolet light (i.e. sunlight, tanning beds) throughout the study
10. Subject is willing to follow study instructions and complete study assessments without assistance and is likely to complete all required visits

Exclusion:

1. Diagnosis of other dermatologic diagnosis that, in the opinion of the investigator, would interfere with diagnosis, examination, or treatment of the studied condition (i.e. psoriasis, atopic dermatitis, lupus, dermatomyositis, seborrheic dermatitis, perioral dermatitis, etc.)
2. Subjects with severe cystic acne, acne conglobate, acne fulminans, or secondary acne (chloracne or drug-induced acne)
3. Uncontrolled systemic disease(s) that, in the opinion of the investigator, would put the patient at significant risk if enrolled in the study or would interfere with subject's participation in the study

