2. Change from baseline in Post Acne Hyperpigmentation Index (PAHPI) at weeks 12, 18, and 24.
3. Change from baseline in Melanin Index (MI) of target lesion at weeks 12, 18, and 24
4. Change from baseline in the proportion of subjects with score of 0 or 1 on ASIS “dark spot” score at weeks 4, 12, 18, and 24.
5. Proportion of subjects with GAAS of 0 (none) or 1 (minimal) at weeks 4, 12, 18, and 24

6. Percent change from baseline in all lesion counts (inflammatory, noninflammatory, and total) at weeks 4, 12, 18, and 24.

f) Procedures Involved in the Human Research

This is a single-center, single-group, open-label study using Aczone® (dapson) gel 7.5%. All subjects will receive the study medication. Aczone® gel is an off-white to yellow gel with suspended particles. It is supplied in an airless pump containing a polypropylene bottle with a high density polyethylene piston. It will be dispensed as a 60g pump.

Subject will apply Aczone® once daily to the entire face. Study drug must not be applied to other areas of the body, including the upper chest, upper back or shoulders.

Prior to the start of the study, potential subjects will be given an IRB-approved Informed Consent Document (ICD) containing a Health Insurance Portability and Accountability Act (HIPAA) disclosure agreement to read, understand, and sign. All questions about the study should be answered to the satisfaction of the candidate subject. They will have all of their study-related questions answered by the PI or designee, and if they agree to participate, the subject will sign two original copies of the ICD. The subjects will retain one original copy and one original copy will be kept in the study file. The subjects who sign an ICD will be assigned a screening number.

After providing informed consent, subjects will be assessed for study eligibility at the Screening visit (day -28 to day -1), which includes review of medical history and concomitant, acne lesion counting and severity ratings, and serum pregnancy test (if applicable). The PI or a medically qualified designee must review this information (i.e. medical history, concomitant medication, and eligibility review) for each subject to confirm their eligibility before enrollment. A total of 20 subjects who meet eligibility criteria will undergo Baseline / Day 0 assessments. Subjects will return for visits at weeks 4, 12, 18, and 24. There will be a phone visit at week 8.

Study Assessments and Efficacy Measures:

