Global Acne Assessment Score (GAAS):

The subject's acne severity will be assessed by the investigator using a 5-point GAAS at screening, baseline, and weeks 4, 12, 18, 24.

Grade	Description
0	None No evidence of facial acne vulgaris
1	Minimal Few noninflammatory lesions are present; a few inflammatory lesions (papules/pustules) may be present; no nodulo-cystic lesions present
2	Mild Several to many noninflammatory lesions are present; a few inflammatory lesions are present; no nodulo-cystic lesions present.
3	Moderate Many noninflammatory and inflammatory lesions are present; no nodulo-cystic lesions are present.
4	Severe Significant degree of inflammatory disease; papules and pustules are a predominant feature; a few nodulo-cystic lesions are present (no more than 2)

Lesion Counts:

The lesion counts, including inflammatory and non-inflammatory lesions, will be performed at screening, baseline, and weeks 4, 12, 18, and 24. Inflammatory lesions (papules, pustules, nodules/cysts) and

noninflammatory lesions (open comedone, closed comedone) will be counted individually. The sum of the inflammatory lesion counts and non-inflammatory lesion counts will be totaled.

ASIS ®:

Acne Symptom and Impact Scale (ASIS ®) will be given to subjects' for completion at baseline and weeks 4, 12, 18, and 24. The ASIS ® contains 9 items assessing symptom severity and 8 items assessing the psychosocial impact of acne vulgaris (6). High scores on the ASIS® indicate the presence of more severe symptoms, whereas higher scores on the ASIS indicate better outcomes on acne health-related quality of life.

PAPHI:

The postacne hyperpigmentation index (PAHPI) has been shown to be a reliable and valid score measuring post-inflammatory hyperpigmentation from acne (7). PAHPI will be scored using the following formula:

Total PAHPI = S + I + N

PAHPI Score can range from 6-22.

Lesion Size (S)

Weighted Score (S)	Median Lesion size
2	<3mm
4	3-6mm
6	7-10mm
8	>10mm

Lesion Intensity (I)

Weighted Score (I)	Median Lesion Intensity
3	Slightly darker than surrounding skin
6	Moderately darker than surrounding skin
9	Significantly darker than surrounding skin

Lesion Number (N)

Weighted Score (N)	Number of Lesions
1	1-15
2	16-30
3	31-45

4	46-60
---	-------

5	>60
---	-----

Melanin Index:

A narrowband reflectance spectrophotometer (mexameter MX-16) will be used to measure the degree of pigmentation of involved and adjacent uninvolved skin of one representative facial PIH lesion (8).

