At each time point, the changes from baseline in ordinal secondary endpoints GAAS, PAHPI, MI, the proportion of subjects with a score of 0 or 1 on ASIS “dark spot,” the proportion of subjects with $GAAS < 2$ will be presented in frequency tables. The (i,j) entries in the tables are counts of subjects in category i at baseline that moved to category j at that time point. A high frequency of counts falling off the main diagonal of the table is evidence in favor of a significant treatment effect. Similarly, to the primary endpoint, we will apply a two-sided paired t-test to assess the significance of changes from baseline in each outcome. We will apply the Bonferroni correction to adjust for the multiplicity of tests. In parallel, we will test pre vs. post differences in these ordinal outcomes with the Wilcoxon Signed Rank test. Discrepancies between the parametric and non-parametric approaches will be discussed on a case basis. In addition to this approach, we will fit an ordinal logit model, including all available time points, age, and gender as covariates.

The changes from baseline in lesion counts (inflammatory, non-inflammatory, and their aggregation) will be assessed with the two-sided paired t-test followed by Bonferroni correction. A Generalized Linear Mixed Model (GLMM) will be fitted to model the count of lesions as the dependent variable, time and inflammation as fixed effects, age, and gender as covariates. In this framework, we will include random intercept and slope for each subject’s trajectory. The contrasts will reveal differences between time points and treatment effect in inflammatory vs. non-inflammatory lesions.

Missing Data and Outliers

Missing data in the longitudinal data analysis will be handled by the mixed-effects approach which performs an appropriate adjustment of the coefficients’ degrees of freedom for each fitted model. We do not foresee issues with outliers due to the endpoints’ measurement level, most of them being ordinal.

Reference:

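### The proportion with GAAS 0 or 1 is tested as a change from baseline, although entry makes its baseline value practically zero; it should be estimated at each visit with an exact interval

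*Combined protocol and SAP*

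**What the plan says.** Section e) Endpoints defines secondary endpoint 5 as "Proportion of subjects with GAAS of 0 (none) or 1 (minimal) at weeks 4, 12, 18, and 24". It is not worded as a change. Secondary endpoint 4, on the ASIS dark spot score, is worded as a change from baseline in a proportion, so the list itself separates the two kinds of endpoint.

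Section k) Statistical Analysis Plan, under Analysis of secondary Endpoints, does not keep that separation. It places the proportion with GAAS below 2 in a list of changes from baseline in ordinal endpoints and plans baseline-by-visit frequency tables. It then states: "we will apply a two-sided paired t-test to assess the significance of changes from baseline in each outcome". A Bonferroni correction follows, then a Wilcoxon signed-rank test of the same outcomes, and then: "we will fit an ordinal logit model, including all available time points, age, and gender as covariates".

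The entry rules bear on the baseline value. Inclusion 4 requires "investigator-assessed Global Acne Assessment Score (GAAS) of 3 or 4 at screening", and inclusion 5 requires "Facial acne vulgaris with 20 to 50 (inclusive) inflammatory lesions and 30 to 100 (inclusive) noninflammatory lesion". The assessment schedule lists the inclusion/exclusion check at both Screening and Baseline. GAAS is rated "using a 5-point GAAS at screening, baseline, and weeks 4, 12, 18, 24", so the baseline score is a second rating.

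**The concern.** If nobody can be a responder at baseline, a pre-post test of the responder proportion compares a value set by the entry rules with whatever is seen later. Change can go in one direction only. The plan reads off-diagonal counts in the frequency tables as evidence of a treatment effect, but in the table for this outcome the baseline row for GAAS below 2 is empty, so any off-diagonal count must be an improvement.

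At stake are four visit-specific t-tests (weeks 4, 12, 18 and 24), their signed-rank counterparts, and possibly a model. A reader could take a small p-value as a finding about response when the useful result is the size of the response rate and its uncertainty. The tests also use up part of the Bonferroni allowance.

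**Working it through.** **1. Is the baseline proportion zero?** The sample-size paragraph assumes a baseline mean of 3.5 and an SD of 0.513. Ten subjects at grade 3 and ten at grade 4 give mean 3.5 and SD = √(20 × 0.5² / 19) = √(5/19) = 0.513, which matches the plan. (The plan's power statement of more than 90% for a 1-point change also holds: power exceeds 0.9999 with 0.513 as the SD of change.) The planning figures thus fit a baseline made up only of grades 3 and 4. The scale points the same way: grade 1 means "Few noninflammatory lesions are present; a few inflammatory lesions (papules/pustules) may be present", which is hard to reconcile with 30 to 100 noninflammatory lesions at entry.

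**2. What the paired tests become.** Let k of n=20 subjects be responders at a visit, with baseline 0 for all. The differences are k ones and 20−k zeros.

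- t-test: mean k/20 and variance k(20−k)/(20×19), so t = √(19k/(20−k)) on 19 df. For k=4, t = √4.75 = 2.18. For k=8, t = √12.67 = 3.56.
- Exact signed-rank test: the zeros drop out and all k remaining signs are positive, so two-sided p = 2 × 0.5^k.

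| k of 20 | t-test p | exact signed-rank p | Clopper-Pearson 95% interval |
|---|---|---|---|
| 1 | 0.33 | 1.00 | 0.1% to 24.9% |
| 4 | 0.042 | 0.125 | 5.7% to 43.7% |
| 5 | 0.021 | 0.063 | 8.7% to 49.1% |
| 6 | 0.010 | 0.031 | 11.9% to 54.3% |
| 8 | 0.0021 | 0.0078 | 19.1% to 63.9% |

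The null of no change means a true response rate of 0%. One responder already disproves it, yet at k=1 neither test is significant. The p-value is only a recoding of k.

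At the 0.05 level the t-test needs 4 responders and the exact signed-rank test needs 6, so they disagree at 4 and 5. The plan does not say which form of signed-rank test is meant; the large-sample form gives 0.0455 at k=4. The promised discussion of discrepancies would then turn on that choice rather than on the data.

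**3. How many responders are needed after Bonferroni?** The plan does not state the family, so this is an assumption. Counting visits in the endpoint list gives GAAS 3 + PAHPI 3 + MI 3 + ASIS 4 + GAAS below 2 4 = 17 tests, threshold 0.05/17 = 0.0029. Adding 3 lesion counts × 4 visits = 12 gives 29 tests, threshold 0.05/29 = 0.0017. The t-test at 8 responders (p=0.0021) passes the first threshold and fails the second. The exact signed-rank test at 8 responders fails both.

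**4. How often would the t-test reach p<0.05?** It needs k≥4. For assumed true response rates, whatever their cause, the binomial chance of at least 4 of 20 is 1.6% at a rate of 5%, 13% at 10%, 35% at 15% and 59% at 20%.

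**5. The logit model.** The baseline log-odds estimate is log(0/20), which has no finite value, so with categorical time no contrast against baseline has one either (quasi-complete separation). Illustrative simulated data (responders 0, 6, 4, 8 and 7 of 20 at baseline and weeks 4, 12, 18 and 24; visits treated as independent in the fit) gave:

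- binary outcome, categorical time, baseline included: time coefficients near 24, SE about 48,000, no convergence;
- binary outcome, linear time, baseline included: converged, slope 0.28 per 4 weeks, SE 0.1;
- binary outcome, post-baseline visits only: converged, SEs 0.3 to 0.8;
- binary outcome, Firth penalised fit, categorical time, baseline included: finite contrasts 2.4 to 3.3, SE about 1.5.

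An ordinal logit on a separately simulated 5-level GAAS, with baseline included, converged.

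**The case against.** Several points against the concern stand.

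- A reader might infer that the logit model cannot be fitted. The documents do not support that. The sentence names neither the dependent variable nor the coding of time. An ordinal logit is most naturally read as a model of the 5-level GAAS, which can be fitted. Only one reading fails: unpenalised, binary outcome, categorical time, baseline included.
- A reader might infer that significance follows automatically from the entry rule, or that the result says nothing about the drug. It does not follow: 4 of 20 responders are needed before any adjustment, and 8 may not be enough after it. The lack of a control is a limit of the whole single-arm study, the primary endpoint included, and not of this analysis alone.
- A reader might take the baseline proportion as fixed at exactly zero. The GAAS criterion is timed at screening, up to four weeks before baseline, and no sentence requires grade 3 or 4 at baseline. The lesion criterion names no visit. With the baseline recheck, zero for practical purposes is the accurate statement.
- The response rate is not left unreported. The frequency tables give the responder count at each visit; only an interval is missing.

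None of this rescues the pre-post tests. They can be computed, but they test a change where the endpoint is a level, against a null that is of no interest.

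**Conclusion.** The concern holds in a limited form. The planned analysis does not match secondary endpoint 5: it tests a change from a baseline that is zero for practical purposes, and the resulting p-values carry no information beyond the responder count. The two planned tests can also disagree on the same count, as with 4 responders (0.042 against 0.125 in the exact form). The logit problem is conditional on how the model is specified, which the plan leaves open.

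The figures assume that all 20 subjects are observed at the visit, as the plan expects, and that none has GAAS 0 or 1 at baseline. The Bonferroni thresholds rest on the assumed families of 17 and 29 tests.

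The scope is one secondary endpoint. The primary analysis, the tests of the 5-level GAAS and the ASIS dark spot proportion, which entry does not restrict, are not affected.

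**What to change.** In section k), under Analysis of secondary Endpoints:

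1. Remove the proportion with GAAS below 2 from the paired t-test and signed-rank list and from the Bonferroni count. Under the assumed families the threshold for the remaining tests eases from 0.05/17 = 0.0029 to 0.05/13 = 0.0038, or from 0.05/29 = 0.0017 to 0.05/25 = 0.0020.
2. Report the number and proportion with GAAS 0 or 1 at weeks 4, 12, 18 and 24 with a Clopper-Pearson interval at a stated level. The plan already uses this method for adverse events, but at 90%, so the level must be given.
3. State the dependent variable and the time coding of the logit model. If the binary outcome is modelled, use post-baseline visits only or a penalised likelihood.

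Keep the responder definition in section e) unchanged. Adding a required 2-grade fall would redefine a protocol endpoint and would be nearly redundant, because going from 3 or 4 to 0 or 1 is already a fall of at least 2 grades. The document is dated February 2022, after the anticipated completion in December 2021. It does not say whether data had been seen, which is a further reason not to redefine the endpoint now.

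The cost is a change of analysis wording, with no new data. Four t-test p-values, and their signed-rank counterparts, would no longer be reported.

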4. Subjects with a history of clinically significant hemolysis, anemia, or enteritis (regional enteritis, ulcerative colitis, pseudomembranous colitis, antibiotic-associated colitis)
5. Subjects with allergy or sensitivity to the study drug or its components
6. Subjects who have not complied with the proper wash-out periods:
 - a. Topical anti-inflammatory medications, salicylic acid, corticosteroids, antibiotics, antibacterials, peroxide-containing products, or retinoids within 2 weeks of baseline
 - b. Systemic antibiotics, corticosteroids, antimalarials or oral dapsone within 4 weeks of baseline

- c. Other anti-acne medication, including isotretinoin or spironolactone, within 6 months of baseline
 - d. Chemical peels or other facial acne procedures (laser therapy, light therapy) within 3 months of baseline
 - e. Treatment with botulinum toxin of any serotype in the face within 6 months of baseline
 - f. Estrogens/Birth control pills must have been started ≥ 90 days prior to baseline and use must be continued during the study without alteration or discontinuation.
7. Pregnant or breastfeeding.
 8. Subjects with evidence of alcohol or substance abuse.
 9. Use of any investigational drug within 4 weeks prior to randomization, or 5 pharmacokinetic/pharmacodynamic half-lives, if known (whichever is longer).

c) Number of Subjects

Up to 40 subjects with acne vulgaris will be screened with a goal of 20 total subjects randomized. All 20 randomized subjects are expected to complete all study procedures. Individuals who provide informed consent and fail to meet all of the inclusion and exclusion criteria during the initial evaluation will be considered a “screening failure.”

d) Study Timelines

The study will consist of 6 in-person visits and one phone visit (7 total visits) over up to 28 weeks (4 week screening period plus 24 weeks enrolled in study). Study visits will be conducted at Screening (Visit 1), Baseline (Visit 2, Week 0), Week 4 (Visit 3), Week 8 phone visit (Visit 4), Week 12 (Visit 5), Week 18 (Visit 6), Week 24 (Visit 7).

Enrollment will occur over a 24-36 month period from January 2018 to December 2020. The study is anticipated to be completed by December 2021.

e) Endpoints

Primary Endpoint:

1. Mean change from baseline to week 12 in Global Acne Assessment Score (GAAS)

Secondary Endpoints:

1. Change from baseline in Global Acne Assessment Score (GAAS) at week 4, 18, and 24.

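### Optional improvement: Holm's step-down instead of single-step Bonferroni for the secondary paired t-tests keeps the same familywise bound and can only add rejections

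*Combined protocol and SAP*

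**What the plan says.** In section k), Analysis of secondary Endpoints, the first paragraph covers GAAS, PAHPI, MI, the ASIS dark-spot responder proportion and the GAAS 0/1 proportion. It plans that "we will apply a two-sided paired t-test to assess the significance of changes from baseline in each outcome" and continues: "We will apply the Bonferroni correction to adjust for the multiplicity of tests". A separate paragraph says that changes in the three lesion counts "will be assessed with the two-sided paired t-test followed by Bonferroni correction". No step-down procedure is named. The number of tests, the family boundaries and the significance level for secondary tests are not stated. The 5% level appears only under Sample Size Considerations, for the primary test.

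The tests can be counted from section e) Endpoints:

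- "Change from baseline in Global Acne Assessment Score (GAAS) at week 4, 18, and 24": 3 tests (week 12 is the primary)
- "Change from baseline in Post Acne Hyperpigmentation Index (PAHPI) at weeks 12, 18, and 24": 3 tests
- "Change from baseline in Melanin Index (MI) of target lesion at weeks 12, 18, and 24": 3 tests
- "Change from baseline in the proportion of subjects with score of 0 or 1 on ASIS" for the dark-spot item, at weeks 4, 12, 18 and 24: 4 tests
- "Proportion of subjects with GAAS of 0 (none) or 1 (minimal) at weeks 4, 12, 18, and 24": 4 tests
- Inflammatory, noninflammatory and total lesion counts, each at weeks 4, 12, 18 and 24: 12 tests

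**The concern.** Single-step Bonferroni holds every p-value to the strictest cut-off, however many other tests in the family have already succeeded. Holm's procedure relaxes the cut-off after each rejection and keeps the same familywise bound. With 20 subjects, and withdrawn subjects not replaced, power on the secondary endpoints is limited, and the sample-size calculation covers only week-12 GAAS. The secondary endpoints also carry the study's additional aim, the effect on hyperpigmentation, through PAHPI, MI and the dark-spot score. At stake is some avoidable loss of power for moderate secondary effects. The validity of the plan is not in question.

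**Working it through.** **The plan's own figure.** Two-sided paired t-test, n = 20, change of 1 grade, SD 0.513, level 5%. The standardised effect is 1/0.513 = 1.95, and noncentral-t power on 19 df exceeds 99.99%. If 0.513 is instead the SD at each visit and visits are uncorrelated, the change SD is 0.513 × √2 = 0.725 and power is 99.99%. The stated power of more than 90% holds. The SAP gives no figure for the secondary adjustment.

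**Family sizes (inferred).** First paragraph: 3 + 3 + 3 + 4 + 4 = 17. Lesion counts: 3 × 4 = 12. A familywise level of 5% is assumed for each.

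**The two procedures.** Bonferroni rejects each p ≤ 0.05/m. Holm orders the p-values and rejects from the smallest upwards while p(i) ≤ 0.05/(m − i + 1). Holm's first cut-off equals Bonferroni's and later ones are larger, so no Bonferroni rejection is lost. With m0 true nulls, a false rejection under Holm requires some true-null p ≤ 0.05/m0. By Boole's inequality that has probability at most 0.05, whatever the dependence. Both methods reject at least once exactly when the smallest p ≤ 0.05/m, so that chance is identical.

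**Observed mean change needed (critical t on 19 df divided by √20).**

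| Cut-off | Critical t | Bar in SD |
|---|---|---|
| 0.05/17 = 0.0029 | 3.409 | 0.762 |
| 0.05/12 = 0.0042 | 3.255 | 0.728 |
| 0.05 (Holm's last step) | 2.093 | 0.468 |

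**Power of one test under Bonferroni** at assumed effects of 0.65, 0.8 and 1.0 SD: 34.5, 57.5 and 83.4% with 17 tests; 39.4, 62.8 and 86.8% with 12.

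**Simulated gain in average power, Holm minus Bonferroni.** Assumptions: 10,000 replicates, n = 20, exchangeable normal changes, correlation 0.3 or 0.6, equal real effects of 0.65 to 1.0 SD.

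| Share of effects real | 17 tests | 12 tests |
|---|---|---|
| About 30% (5 of 17; 4 of 12) | 1.3-2.3 points | 1.7-2.7 points |
| About 60% (10 of 17; 7 of 12) | 3.7-6.0 points | 4.0-5.9 points |
| All | 9.9-16.8 points | 8.6-16.2 points |

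At 0.8 SD, real effects detected over both blocks, Bonferroni against Holm:

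- 5.4 against 5.6 of 9
- 10.0-10.1 against 11.0-11.1 of 17
- 17.2-17.4 against 21.7-22.0 of 29

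Simulated familywise error per family was 1.5-3.3% for Bonferroni and 2.6-4.6% for Holm.

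**GAAS 0/1.** Entry requires GAAS 3 or 4 at screening, so assume that nobody scores 0 or 1 at baseline. With k responders of 20, the paired t-test on the 0/1 change has mean k/20 and variance k(20 − k)/(20 × 19). For k = 8, t = 0.4/√(0.2526/20) = 3.56 and p = 0.0021. Likewise k = 7 gives 0.0047 and k = 4 gives 0.042. Bonferroni needs 8 responders. Holm needs 8 at the first step, 7 from step 8 (0.05/10 = 0.005) and 4 at the last.

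**Where the gain is negligible.** For a 1-point GAAS change, power at 0.05/17 is already 99.3% with SD 0.725 and over 99.9% with SD 0.513.

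**The case against.** The strongest case against raising this is that Bonferroni is a standard, valid choice, and these are secondary endpoints of a 20-subject open-label study. That stands, and it is why the point is optional.

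Four further objections also stand and limit the claim:

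- **Bonferroni gives something more.** A reader might infer that it costs power for no stronger guarantee. That is not so. It also bounds the expected number of false rejections at 0.05 per family (at most m × 0.05/m), and Holm does not. With 17 true nulls, simulation gave 0.052 (Bonferroni) against 0.057 (Holm) at correlation 0.6, and 0.051 against 0.074 at 0.9. Bonferroni also has matching simultaneous intervals.
- **Only the bound is the same.** Holm's attained error rate is higher. The 5% applies per family; over two families the bound is 10% with either method.
- **The 17/12 split is inferred.** The secondary analysis is introduced visit by visit, so per-visit families of 3 to 5 tests are readable, as are per-outcome families of 3 or 4. With 5, 4 or 3 tests the Bonferroni bar is 0.64, 0.62 or 0.59 SD. The Holm gain at 0.8 SD with all effects real is then about 7-12 points, against about 14-17 for 17/12.
- **Timing.** The document is dated 7 February 2022, and Study Timelines anticipates completion by December 2021. The documents do not confirm actual completion. If secondary results were already visible, a switch that can only add rejections would be a post hoc relaxation.

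The simulation is also simplified: 8 of the 17 tests are binary, and total lesions is the sum of two other tested counts. This affects the size of the gain. It does not affect Holm's dominance within a fixed family.

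**Conclusion.** This is a cheap, optional improvement. On any fixed family, Holm keeps the 5% familywise bound under any dependence and loses no Bonferroni rejection. Its size is less certain. On the 17/12 reading, with equal assumed effects of 0.65 to 1.0 SD and correlation 0.3 to 0.6, average power rises by about 1-3 points if 30% of effects are real, 4-6 if 60%, and 9-17 if all are. The top of that range needs every effect to be real. The gain is zero if no p-value in a family passes 0.05/m, and smaller if the sponsor intended smaller families.

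A reader might infer that the SAP's multiplicity control is wrong or that the primary result is affected. The documents support neither: Bonferroni controls familywise error as planned, and the primary test lies outside these paragraphs.

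**What to change.** In both sentences of Analysis of secondary Endpoints, replace *Bonferroni correction* with *Holm step-down (Bonferroni-Holm) correction*. Apply it to the planned paired t-tests only, at the same level and within the family the sponsor intended. The family must not change with the method, because the guarantee that no rejection is lost holds only within the same family. Holm needs m, so the edit should state each family and its size.

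Settle this before secondary results are examined. If they have already been seen, keep Bonferroni as the planned analysis and report Holm as a labelled supplementary result.

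The cost is a wording change in two sentences, with no new data and no change of test. Three things are given up: simple matching simultaneous intervals, some of the gap between attained familywise error and 5%, and Bonferroni's bound on the expected number of false rejections. Any intervals for secondary changes would be reported unadjusted and labelled so. The only intervals the SAP names are the 90% Clopper-Pearson intervals for adverse events, which are untouched.

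### The lesion-count model omits the term its promised contrast needs, and no analysis is assigned to the declared percent-change endpoint

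*Combined protocol and SAP*

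**What the plan says.** - **Declared endpoint** (section e, secondary endpoint 6): "Percent change from baseline in all lesion counts (inflammatory, noninflammatory, and total) at weeks 4, 12, 18, and 24".
- **Assigned test** (section k, Analysis of secondary Endpoints): "The changes from baseline in lesion counts (inflammatory, non-inflammatory, and their aggregation) will be assessed with the two-sided paired t-test", with Bonferroni correction. Percent change is not mentioned anywhere in section k.
- **Model** (same paragraph): a GLMM with the lesion count as the dependent variable and "time and inflammation as fixed effects, age, and gender as covariates". For the random part: "In this framework, we will include random intercept and slope for each" subject. No distribution or link is given.
- **What the model is to deliver:** "The contrasts will reveal differences between time points and treatment effect in inflammatory vs. non-inflammatory lesions".
- **Design** (section f): "This is a single-center, single-group, open-label study".
- **Eligibility** (section b, inclusion criterion 5): "20 to 50 (inclusive) inflammatory lesions and 30 to 100 (inclusive) noninflammatory lesion".

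**The concern.** There are two separate problems in one paragraph of the plan.

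**The model.** With no control group, a treatment effect can only mean change over time. Comparing it between lesion types means asking whether the two types change by different amounts, which is a time-by-type interaction. A model with only main effects for time and type assumes that the two change equally, so it cannot answer the question it is given.

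**The endpoint.** Change in counts and percent change are different quantities. A fall from 20 to 10 and a fall from 50 to 40 are both 10 lesions, but they are 50% and 20%. A mean change in counts gives more weight to subjects with high baselines. If the plan is followed literally, endpoint 6 is never analysed in its declared form, and someone would have to choose the percent-change method after seeing open-label data.

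**Working it through.** **The plan's own figure.** The documents give no power or precision figure for lesion counts. The only one is the power above 90% for the primary GAAS t-test (n = 20, change 1, SD 0.513, two-sided 5%). It reproduces: a noncentral-t calculation gives more than 99.9%, whether 0.513 is the SD of the change or the per-visit SD with uncorrelated visits. Nothing below depends on it.

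**Part 1: the contrast.** Write the linear predictor for visit *t* and lesion type *k* (1 inflammatory, 0 non-inflammatory) as listed:

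η(t,k) = β₀ + τ(t) + γk + age + gender + b₀ + b₁t

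where b₀ and b₁ are the subject's random intercept and slope. The promised contrast is

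[η(t,1) − η(0,1)] − [η(t,0) − η(0,0)] = [τ(t) − τ(0) + b₁t] − [τ(t) − τ(0) + b₁t] = 0.

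The subject terms are shared by both types and cancel. With an interaction δ(t)k added, where δ(0) = 0, the contrast becomes δ(t), which can be estimated at weeks 4, 12, 18 and 24.

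Two numerical checks on simulated data (assumed inputs, 20 subjects, 5 visits):
- A linear mixed model on log(count + 0.5), with subject intercept and slope, age and gender, and a true week 12 between-type difference of 0.336 in log ratio. The main-effects contrast was 9×10⁻¹⁶.
- A log-link Poisson GEE with baselines 30 and 50 and week 12 falls of 50% and 25% (true log contrast −0.405). The main-effects fit gave about 39% for both types and a contrast of 0. The interaction fit gave 54.8% and 29.6%, and a contrast of −0.443.

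*Size.* Assume baseline means of 30 and 55 and true falls of 50% and 30%, so week 12 means of 15 and 38.5. Fit main effects to these four cells:

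| Model | Inflammatory fall | Noninflammatory fall |
|---|---|---|
| Assumed truth | 50% | 30% |
| Poisson, log link: (15 + 16.5)/85 | 37.1% | 37.1% |
| Negative binomial, log link (dispersion 0.05 to 0.5) | 39.2–40.6% | 39.2–40.6% |
| Gaussian, identity link: 15.75/30.375 and 15.75/54.625 | 51.9% | 28.8% |
| Poisson, identity link | 51.1% | 28.5% |

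The back-transformed Poisson log-link changes are −45 × 31.5/138.5 = −10.2 and −93.5 × 31.5/138.5 = −21.3 lesions, against true −15 and −16.5. They differ only because the two levels differ.

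Over five assumed baseline pairs (30/55, 25/45, 30/80, 40/55, 35/65), the log link gives 36–41% for both types. Gaussian identity gives 47–61% and 25–33%, and Poisson identity 48–55% and 23–33%.

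**Part 2: counts against percent.** Inputs are the eligibility ranges 20–50 and 30–100.
- *Weights.* At the same percent fall, the ratio of contributions to mean count change reaches 50/20 = 2.5 and 100/30 = 3.3.
- *Reported quantity.* If percent response is unrelated to baseline, the two summaries agree within a lesion type. Otherwise assume baselines uniform on [a, b] with midpoint m, and a percent fall linear in baseline with total swing s. Mean count fall divided by mean baseline then differs from the mean percent fall by s(b − a)/(12m).
  - Inflammatory, s = 40 points: 40 × 30/(12 × 35) = 2.9, so 50% reads as 47.1–52.9%.
  - Noninflammatory, s = 40 points: 40 × 70/(12 × 65) = 3.6, so 30% reads as 26.4–33.6%.
  - s = 20 points: 48.6–51.4% and 28.2–31.8%.
- *Test verdicts.* Simulated trials assumed n = 20, uniform baselines, percent fall with SD 30 points capped at 100%, mean fall 15–50%, and alpha 0.05 or 0.05/12 (3 counts × 4 visits), with 5000 trials per setting. Raw and percent tests disagreed in 0–7.8% (inflammatory) and 0–10.1% (noninflammatory), and in at most 1.1% once the mean fall was 40% or more.

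**The case against.** **On the model.** The paragraph is an outline that names factors, not a formula, and it does not exclude an interaction. An analyst told to produce that contrast would have to add the term. The contrast is also not a declared endpoint, the type-specific paired t-tests are untouched, and the visible distortion depends on an unstated link: the identity-link fits at 30/55 come close to the assumed truth. All of this is fair, and it makes the point minor on its own. But a plan that lists the fixed effects, covariates and random terms, and leaves out the one its stated contrast needs, should be completed.

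**On the endpoint.** Endpoint 6 is the only lesion-count endpoint, so the paragraph is evidently meant for it, and change from baseline may be loose shorthand for percent change. A log-link GLMM would also give ratios of mean counts. Neither closes the gap. A paired t-test on counts most naturally means raw differences. No link is stated, a ratio of model means is not the mean of per-subject percent changes, and the plan does not tie that model to endpoint 6.

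**On size.** Test verdicts rarely change, and percent change can be computed from counts already collected. That stands, and it limits the harm to the reported quantity. The exact choice of test for percent change is partly preference; naming percent change as the analysed variable is not.

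**Conclusion.** Both parts hold. The zero contrast is algebra and needs no assumption beyond taking the listed terms as the model. The interaction may have been intended, but it is not written. The endpoint mismatch is textual, and it carries the weight: a declared secondary endpoint has no analysis in its declared form.

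The consequences are moderate, and their sizes rest on assumed baselines, falls and variability that the documents do not give. The error lies mainly in what is reported: a shift of about 3 to 4 points under a strong assumed dependence on baseline, and none if percent response is unrelated to it. The primary analysis, the sample size and the type-specific t-tests on counts are unaffected. The plan should be corrected.

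**What to change.** 1. **Model.** Add the time-by-lesion-type interaction. State the distribution and link, for example a count distribution with log link. Define the between-type contrast as that interaction, at each visit or as a difference in slopes if time is linear, and report the estimate with its interval.
2. **Endpoint 6.** Test each subject's percent change in inflammatory, noninflammatory and total counts at weeks 4, 12, 18 and 24 with a one-sample t-test against zero and a signed-rank check, under the planned Bonferroni correction. The raw-change t-tests can stay as supportive. Rewording endpoint 6 as change in counts would also reconcile the sections, but it would alter a declared endpoint.

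**Cost.** Some plan wording and a short analysis. No new data are needed: "The lesion counts, including inflammatory and non-inflammatory lesions, will be performed at screening, baseline, and weeks 4, 12, 18, and 24". The minimum counts of 20 and 30, with eligibility rechecked at baseline, rule out a zero denominator. If the raw-change tests sit outside the Bonferroni family, the number of adjusted tests does not rise.

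The interaction adds 1 parameter (linear time) or 4 (categorical visits). It widens type-specific intervals by √(2/(1 + ρ)) if the two types have equal standard errors and correlation ρ: 41% at ρ = 0, 15% at 0.5, 5% at 0.8.

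Power for the between-type contrast is limited. For falls of 50% against 30% (log(0.5/0.7) = −0.336), n = 20 and two-sided 5%, it is about 95%, 66% or 43% if the SD of the within-subject difference in log ratios is 0.4, 0.6 or 0.8 (assumed). The 95% half-widths on the log scale are then 0.19, 0.28 and 0.37, so the contrast is best reported as an estimate.
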